16.35 Data & Safety Monitoring

16.351 The principal investigator(s) and the study statistician will review the study at least every quarter to identify accrual, adverse events, and any endpoint problems that might be developing. The Mayo Clinic Cancer Center (MCCC) Data Safety Monitoring Board (DSMB) is responsible for reviewing accrual and safety data for this trial at least twice a year, based on reports provided by the MCCC Statistical Office.

16.352 Adverse Event Stopping Rule (to be evaluated in each cohort independently): The stopping rule specified below is based on the knowledge available at study development. We note that the rule may be adjusted in the event of either (1) the study re-opening to accrual or (2) at any time during the conduct of the trial and in consideration of newly acquired information regarding the adverse event profile of the treatments under investigation. The study team may choose to suspend accrual because of unexpected adverse event profiles that have not crossed the specified rule below.

Accrual will be temporarily suspended to the cohort if at any time we observe events considered at least possibly related to study treatment (e.g., an adverse event with attribute specified as "possible," "probable," or "definite") that satisfy either of the following:

- If 3 or more of the first 12 treated patients experience a grade 4 or higher non-hematologic adverse event (except infusion related reactions) at least probably related to treatment except infusion related reactions.
- If after the first 12 patients have been treated, 25% of all patients experience a grade 4 or higher non-hematologic adverse event (except infusion related reactions) at least probably related to treatment.

We note that we will review grade 4 and 5 adverse events deemed "unrelated" or "unlikely to be related," to verify their attribution and to monitor the emergence of a previously unrecognized treatment-related adverse event.

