Overall design: This is a phase II clinical trial of two novel drugs (daratumumab and hyaluronidase given SC and ibrutinib given orally) for treatment of patients with relapsed or refractory CLL. During the first cycle of the treatment, patients are given daratumumab as a single agent (for conduct of correlative studies – please see section 7.0), and starting cycle 2 patients will have both ibrutinib and daratumumab given together. Patients will be grouped in independent cohorts based upon whether they previously received a BTK inhibitor (Cohort 1) vs. BTK inhibitor naïve (Cohort 2). A total of 52 eligible patients will be enrolled in two separate cohorts (i.e. Cohort 1 and 2). A total of 25 cycles (including the first cycle with single agent daratumumab) will be given. The primary goal is to determine ORR of this regimen in each arm.

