16.0 Statistical Considerations and Methodology

16.1 Overview:

This is a Phase II study designed to assess the overall response rate of daratumumab and ibrutinib for relapsed/refractory CLL in two groups independently: Previously received Ibrutinib (Cohort 1) and Ibrutinib naïve (Cohort 2).

16.11 Primary Endpoint:

The primary endpoint in each cohort is the overall response rate after 6 cycles of treatment with daratumumab in combination with ibrutinib (end of Cycle 7). All patients meeting the eligibility criteria who have signed a consent form and have begun treatment will be evaluable for overall response, with the exception of patients who are determined to be a major treatment schedule violation.

16.12 Sample Size:

The phase II study design to be used in each group is fully described in section 16.2. A maximum of 22 evaluable Cohort 1 and 26 evaluable Cohort 2 patients will be accrued unless undue toxicity is encountered. We anticipate accruing an additional 4 patients (2 Cohort 1, 2 Cohort 2) to account for ineligibility, cancellation, major treatment violation, or other reasons. Maximum projected accrual is 52 patients overall.

16.13 Accrual Rate and Study Duration:

The anticipated accrual rate is approximately 2-3 patients per month. Therefore, the accrual period for this phase II study is expected to be about 2 years. The maximum total study duration is expected to be approximately 7 years, or until the last patient accrued has been observed for at least 5 years. The earliest date anticipated for presentation of results is at approximately 2.5 years, or when the last patient accrued has completed the cycle 7 response assessment.

16.2 Statistical Design:

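### The numeric cohort-level safety limits in 16.352 can only suspend accrual, so a limit crossed after a cohort is full requires nothing, with roughly 36-48% of treatment time still to come

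*Combined protocol and SAP*

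**What the plan says.** Section 16.352 is titled a stopping rule and applies to each cohort separately. Its operative sentence begins "Accrual will be temporarily suspended to the cohort if at any time we observe events", and two limits follow. The first is "If 3 or more of the first 12 treated patients experience a grade 4 or higher non-hematologic adverse event" that meets the stated attribution, infusion-related reactions excepted. The second is "If after the first 12 patients have been treated, 25% of all patients experience a grade 4 or higher non-hematologic adverse event" on the same terms. No other consequence is named, and patients already on treatment are not mentioned. A discretionary power sits beside the rule and is also about accrual: "The study team may choose to suspend accrual because of unexpected adverse event profiles that have not crossed the specified rule below".

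Section 16.351 has the investigator and statistician review the study, adverse events included, at least quarterly. It adds that the "Data Safety Monitoring Board (DSMB) is responsible for reviewing accrual and safety data for this trial at least twice a year". Neither review has a threshold or a required action.

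On timing, 16.13 states that "the accrual period for this phase II study is expected to be about 2 years", at 2-3 patients per month. Section 1.3 states: "A total of 25 cycles (including the first cycle with single agent daratumumab) will be given". Section 7.2 fixes the cycle at 28 days. Section 16.324 collects adverse events until 30 days after the last dose.

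**The concern.** The rule may be evaluated at any time, but its consequence exists only while the cohort is recruiting. Planned treatment (about 23 months) is nearly as long as planned accrual (about 24 months), so much of the exposure to the combination comes after the consequence has lapsed. If related Grade 4-5 non-hematologic events reached the plan's own 25% limit in that period, no one would be obliged to do anything because the limit had been reached.

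The protocol says in 1.3 that daratumumab has not yet been studied clinically in CLL. The late toxicity of this combination is therefore not known from earlier trials, and the limits should still have some effect while patients are being treated.

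**Working it through.** **1. Inputs.** Maximum accrual is 52, as 22 + 2 and 26 + 2 patients (16.12). The rate is 2-3 per month and the accrual period about 2 years (16.13). Treatment is 25 cycles (1.3), or up to cycle 24 (4.1, 7.2 and Table 8.3), with 28-day cycles (7.2).

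**2. The plan's accrual figure.** 52/2 = 26.0 months, 52/2.5 = 20.8 and 52/3 = 17.3. The stated 2 years lies within this range. The plan gives no operating table for the 16.352 limits, so there is none to reproduce.

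**3. Treatment length.** 25 × 28 = 700 days, which is 23.0 months at 30.4375 days per month. 24 × 28 = 672 days, or 22.1 months.

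**4. Share of planned treatment time after accrual closes, no dropout.** Let entry be uniform over A months and treatment last D months. The share is D/(2A) if D ≤ A, and 1 − A/(2D) otherwise. For 25 cycles and A = 24, this is 23.0/48 = 0.479.

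| Accrual period (months) | 25 cycles | 24 cycles |
|---|---|---|
| 26.0 (2 per month) | 44% | 42% |
| 24 (as stated) | 48% | 46% |
| 20.8 (2.5 per month) | 55% | 53% |
| 17.3 (3 per month) | 62% | 61% |

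At A = 24 and 25 cycles, 23.0/24 = 96% of 52, about 50 patients, would still have treatment to come at closure if nobody had left.

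**5. With dropout (assumption, not in the documents).** Let discontinuation be exponential with median m, so h = ln 2/m. Mean time on treatment is (1 − e^(−hD))/h. The time before closure is the same expression with D replaced by min(A − entry time, D), averaged over entry. For A = 24 and 25 cycles:

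- m = 12 months: mean time on treatment 12.73 months, of which 7.94 before closure. Share = 1 − 7.94/12.73 = 0.376.
- m = 24 months: 16.80 and 9.64 months. Share = 1 − 9.64/16.80 = 0.426.

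With 24 cycles the shares are 0.365 and 0.411. The range is about 36-43%.

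**6. Whether another provision fills the gap.**

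| Provision | Continues after accrual? | Tied to the 16.352 limits? |
|---|---|---|
| Discretionary suspension (16.352) | Accrual only | No |
| Undue toxicity (16.12) | Accrual only | No |
| Quarterly team review (16.351) | Yes | No |
| DSMB review at least twice a year (16.351) | Yes | No |
| Toxicity weighed in a decision to terminate (16.23) | Yes | No |
| Duty to report a clinically important rise in a serious reaction rate (10.0, 10.32, 10.89e) | Yes | No numeric limit |
| Expedited reporting (10.41, 10.52) | Yes | No; acts on single events |
| Holds and discontinuation (7.7 to 8.3, 13.3) | Yes | No; act on single patients |

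**7. Illustration only.** The share of treatment time is not the chance that a limit is first crossed late. To gauge that chance I simulated cohorts of 24 and 28 patients entering over 24 months, with qualifying events spread evenly over 23 months of treatment. At an assumed true rate of 25%, a limit was first met during accrual in about 39-46% of cohorts and only after the cohort was full in about 26-33%. At a rate of 10%, each figure was about 5-7%. Neither the rates nor the even spread comes from the documents.

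**The case against.** The strongest reply is that safety oversight plainly continues. Section 8.2 holds daratumumab for most Grade 3 or higher non-hematologic toxicity and holds or omits ibrutinib for other Grade 4 events. These are the kind of events that 16.352 counts. Serious Grade 4-5 events need 24-hour notice (10.41). The sponsor must report a clinically important rise in the rate of a serious suspected reaction, which is a study-level duty independent of accrual. The team must look at adverse events every quarter. All of this stands, and it rules out two stronger readings.

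A reader might infer that the trial has no mandatory safety mechanism after accrual. The documents do not support that: what lapses is the effect of the numeric cohort limits. A reader might also infer that dosing could go on for up to six months without any required review. That is wrong too, because the quarterly team review is required. Six months is the longest interval only for the independent board, which "is responsible for reviewing accrual and safety data for this trial at least twice a year", and that frequency is a minimum.

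Three further replies have some force. Section 1.2 reports that most ibrutinib events of interest fell or stayed level over three years, so an even spread of events is not a neutral assumption; that evidence, however, concerns ibrutinib and not the combination. The DSMB's operating procedures are not in the documents, so it may already be able to meet unscheduled. But nothing in the plan requires the team to tell it that a limit has been crossed. Finally, this is a design choice and not a contradiction. That is true, but a stated safety limit that does nothing for a large part of treatment is worth a short amendment.

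**Conclusion.** The point holds at cohort level. The 16.352 limits are the only numeric cohort-level safety limits in the plan. Their single consequence is empty once a cohort is full, and no continuing provision ties them to a required action.

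The exposed share of treatment time is 48% with 25 cycles, 24 months of uniform accrual and no dropout, and 46% with 24 cycles. It is 42-62% over the stated accrual rates without dropout, and about 36-43% at 24 months' accrual under the assumed dropout. These figures treat the two cohorts as filling together. A cohort that filled in 12 or 18 months would have 74% or 61% still to come (25 cycles, no dropout); one that took longer than 24 months would have less than 48%.

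The documents also disagree on treatment length: 25 cycles in 1.3, cycle 24 in 4.1, 7.2 and Table 8.3, and treatment until progression in the 7.2 footnote and the 7.3 dosing table. These passages must be reconciled. Treatment until progression would tend to raise the share.

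How often a limit would first be crossed late cannot be determined from the documents, because no expected rate of qualifying events is given.

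**What to change.** Keep both limits and add to 16.352: *The limits are evaluated in all treated patients in the cohort until the last patient's 30-day adverse event window closes. If a limit is crossed after accrual to the cohort is complete, the study team promptly notifies the MCCC DSMB, which holds an unscheduled review of the cohort's safety data.*

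This uses the existing board, the existing Statistical Office reports and the adverse event window already in 16.324. It is procedural only and sets no new threshold, dose or treatment-stopping rule. The cost is two sentences and a possible unscheduled DSMB review.

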Undoubtedly, CD38 is an important target whose functional activity can be mitigated with anti-CD38 mAbs such as daratumumab and whose anti-tumor effect may be enhanced when used in combination with ibrutinib. Biologically this combination is highly attractive and anticipated to enhance anti-CLL effects. Notably, we have observed that ibrutinib treatment of malignant lymphoid cells does not downregulate CD38 surface receptor levels and thus unlikely to

compromise the binding and therapeutic impact of daratumumab (Manna et al ASH 2017). No clinical study has been done to date to evaluate the role of daratumumab in the management of CLL. Given the target (CD38) is equally expressed in CLL patients, it is highly relevant to explore daratumumab's therapeutic potential in these patients and its combination with ibrutinib. We hypothesize that daratumumab engages CD38 signaling, induces death in malignant B CLL and thus can be developed as an effective CLL therapeutic. This proposal focuses on this novel strategy to treat CLL patients using daratumumab to enhance the efficacy of currently established and approved therapeutic *ibrutinib*. To address this the clinical trial is designed to enroll patients with relapsed or refractory CLL, in these adult patients ibrutinib is an effective and approved treatment, however most patients with this agent only achieve partial remission as is noted in section 1.2. Clearly to make a larger impact on the clinical course of the disease to enhance the depth of clinical response (such as achieving MRD) new combination will be required to boost the effect of existing therapy and the design of this study addresses this critical aspect.

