10.52 Death

Note: A death on study requires both routine and expedited reporting regardless of causality, unless as noted below. Attribution to treatment or other cause must be provided.

Any death occurring within 30 days of the last dose, regardless of attribution to an agent/intervention under an IND requires expedited reporting within 24-hours.

Any death occurring greater than 30 days with an attribution of possible, probable, or definite to an agent/intervention under an IND requires expedited reporting within 24-hours.

Reportable categories of Death

- Death attributable to a CTCAE term.
- Death Neonatal: A disorder characterized by cessation of life during the first 28 days of life.
- Death NOS: A cessation of life that cannot be attributed to a CTCAE term associated with Grade 5.
- Sudden death NOS: A sudden (defined as instant or within one hour of the onset of symptoms) or an unobserved cessation of life that cannot be attributed to a CTCAE term associated with Grade 5.
- Death due to disease progression should be reported as **Grade 5 “Disease Progression”** under the system organ class (SOC) of the **General disorders and administration site conditions**. Evidence that the death was a manifestation of underlying disease (e.g.), radiological changes suggesting tumor growth or progression: clinical deterioration associated with a disease process) should be submitted.

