1. Daratumumab can cause severe infusion reactions, usually during the first infusion. Patients who have experienced a reaction may experience further reactions with subsequent infusions. Most reactions occur during or within 4 hours of infusion, however may occur up to 48 hours after an infusion. Warn patient of this possibility. Monitor patient throughout infusion for bronchospasm, hypoxia, SOB, and hypertension. Patients may also

experience symptoms of anaphylaxis. Administer emergency medication as ordered.

2. Patients may experience infections, including URI and pneumonia. Patients who have an ongoing infection should not receive agent.
3. Patients may experience gastrointestinal side effects including diarrhea and nausea. Treat symptomatically and monitor for effectiveness.
4. Warn patients about the possibility of peripheral neuropathy, dizziness, and insomnia.
5. Fatigue is common. Instruct patient in energy conserving lifestyle.
6. Rarely patients may experience cardiac issues including, atrial-fibrillation, peripheral edema, and hypertension. Instruct patient to report any chest pain, heart palpitations, and swelling to the study team.
7. Monitor CBC w/diff as cytopenias (thrombocytopenia, neutropenia, anemia, and lymphopenia) have been seen. Instruct patient to report any unusual, bruising, bleeding and/or infections/fever to the study team.
8. If using SC, injection should be in the abdomen over 3-5 minutes. There is no data on SC injections on other parts of the body.

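### The only mandatory accrual-suspension rule (16.352) never counts a related death from an infusion reaction or hematologic event, weighs other deaths like grade 4 events, and states two attribution thresholds

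*Combined protocol and SAP*

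**What the plan says.** Section 16.352 is applied to each cohort separately. Its lead-in reads "Accrual will be temporarily suspended to the cohort if at any time we observe events considered at least possibly related to study treatment". Two triggers follow.

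- **First 12 patients:** "If 3 or more of the first 12 treated patients experience a grade 4 or higher non-hematologic adverse event (except infusion related reactions". The sentence closes by setting the attribution level and repeating the exception: "at least probably related to treatment except infusion related reactions".
- **After 12 patients:** "If after the first 12 patients have been treated, 25% of all patients experience a grade 4 or higher non-hematologic adverse event", with the same infusion-reaction exception and the same *probable* attribution level.

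The section also has a permissive clause: "The study team may choose to suspend accrual because of unexpected adverse event profiles that have not crossed the specified rule below". It adds a check on the attribution of grade 4 and 5 events judged unrelated or unlikely to be related.

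Elsewhere, Appendix V makes a death from hematologic toxicity a grade 5 event. Section 10.52 states "Any death occurring within 30 days of the last dose, regardless of attribution to an agent/intervention under an IND requires expedited reporting" and gives 24 hours for that report. Section 1.3 states "No clinical study has been done to date to evaluate the role of daratumumab in the management of CLL", and the nursing guidelines in 15.19 warn "Daratumumab can cause severe infusion reactions, usually during the first infusion".

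**The concern.** It is reasonable for a stopping rule to set aside infusion reactions and cytopenias, which are expected with these agents and usually manageable. That reasoning does not carry over to a fatal event, yet the exclusions here have no upper grade. Other related deaths do count, but with the weight of a single grade 4 event.

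The plan describes this as the first clinical evaluation of daratumumab in CLL, so there is no earlier CLL experience to lean on. If a patient dies of a treatment-related cause, nothing in the plan requires enrollment to pause while the death is reviewed.

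**Working it through.** The plan states no operating characteristics for this rule, so there is no figure of its own to reproduce.

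**1. What each kind of related death contributes to the rule**

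| Grade 5 event | Counts toward 16.352? | Reason |
|---|---|---|
| Infusion related reaction | No | Excepted in both triggers at every grade |
| Hematologic toxicity | No | Rule covers non-hematologic events only; Appendix V grades such a death 5 |
| Other, probable or definite | Yes, as one patient | Grade 4 or higher |
| Other, possible | Unclear | Lead-in includes it, both triggers leave it out |

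The boundary of *hematologic* also matters. The ibrutinib table in 8.2 places febrile neutropenia under blood and lymphatic disorders, so a death coded there could go uncounted. Hemorrhage is recorded under general disorders (10.61), so a fatal bleed would probably count.

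**2. Most qualifying patients without an obligatory hold**

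The second trigger does not say *or more*; I read it as at least 25%. The threshold at n patients is then 0.25n rounded up, and the largest count without a hold is one less.

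- First 12: threshold 3, so 2.
- n = 22: 0.25 × 22 = 5.5, threshold 6, so 5 (5/22 = 23%).
- n = 26: 0.25 × 26 = 6.5, threshold 7, so 6 (6/26 = 23%).

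All of these could be deaths. Because the cohorts are judged separately, 2 in the first 12 of each gives 4 of 24 (17%) with no trigger. For infusion-reaction or hematologic deaths there is no limit.

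**3. How often the rule fires**

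First 12: P(X ≥ 3), X ~ Binomial(12, p). Full rule: exact sequential enumeration, stopping at 3 or more events while n ≤ 12, and at a count of at least 0.25n afterwards. The rates p are assumed.

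| True qualifying-event rate | First 12 | Full rule by 22 | Full rule by 26 |
|---|---|---|---|
| 2% | 0.0015 | 0.0016 | 0.0016 |
| 5% | 0.020 | 0.022 | 0.022 |
| 10% | 0.11 | 0.13 | 0.13 |
| 20% | 0.44 | 0.54 | 0.56 |

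These are rates of all qualifying events. They are rates of death only if every qualifying event is a death.

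**4. What can happen between scheduled reviews**

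Section 16.13 expects 2–3 patients per month. Between quarterly team reviews that is 3 × 2 to 3 × 3, or 6–9 patients; between twice-yearly DSMB reviews it is 6 × 2 to 6 × 3, or 12–18. Both are maximum gaps, since 16.351 says *at least* for each.

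**5. Cost of a hold after any related death**

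Chance of at least one related death in N patients: 1 − (1 − d)^N, with assumed death rate d. N = 52 is the projected maximum; 24 and 28 are the cohorts with their 2 extra patients each.

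| d | N = 24 | N = 28 | N = 52 |
|---|---|---|---|
| 1% | 21% | 25% | 41% |
| 2% | 38% | 43% | 65% |
| 5% | 71% | 76% | 93% |

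These somewhat overstate the chance of a pause, because a death after accrual closes cannot interrupt it.

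**The case against.** The strongest reply is that the plan surrounds this rule with other safeguards.

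- Serious grade 4 and 5 events are reported within 24 hours (10.41).
- Infusion reactions of grade 3 or higher and cytopenias of grade 4 or higher, largely the two excluded categories, are reported within 3 business days whether serious or not (10.83).
- The team reviews the study at least quarterly and the DSMB at least twice a year (16.351).
- Accrual proceeds only absent undue toxicity (16.12), toxicity informs any decision to terminate (16.23), and 16.352 allows the rule to be adjusted at any time.
- Under 10.2, an event more severe than listed is unexpected, so a fatal infusion reaction could well fall within the discretionary clause.

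All of this stands. A reader might infer that the rule is blind to deaths, or that accrual could not be stopped after one. The documents do not support that. The fatal toxicities the plan describes, such as arrhythmia, cardiac failure, infection, stroke and hepatitis B reactivation, are non-hematologic and count if attribution is met. The plan reports no fatal daratumumab infusion reaction, and the warning in 15.19 is worded for infusions while this trial injects subcutaneously.

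A reader might also take the 11% and 44% trigger probabilities as proof of a weak rule. They are not: those true rates lie below the 25% limit, where infrequent triggering is what the rule intends.

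What the reply does not supply is any provision that makes a hold mandatory after a related death. It also leaves the conflict over attribution untouched.

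**Conclusion.** The gap is real but bounded. Suspension after a related death is possible under several provisions and obligatory under none, unless that death completes the count in 16.352. Deaths from infusion reactions or hematologic events can never contribute to the count. Other qualifying deaths contribute one patient each, up to 2 in a cohort's first 12, 5 of 22 or 6 of 26 without an obligatory hold. These are the most the rule tolerates, not expected numbers; the documents give no related-death rate.

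The two attribution levels are a plain contradiction in the text. Under the stricter one, a death judged possibly related does not count.

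One might go further and ask that a single death stop both cohorts. The plan does not compel that: the rule is written per cohort, and the calculation above shows that a single-death trigger could fire often even at modest death rates. A hold in the affected cohort, with the other considered at the same review, closes the gap.

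**What to change.** Amend 16.352 in three places.

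1. Use one attribution threshold in the lead-in and both triggers. The sponsor must decide which; the passages cannot both stand.
2. Limit the infusion-reaction and hematologic exclusions to events below grade 5.
3. Add a bullet: any grade 5 event meeting the reconciled threshold temporarily suspends accrual to the affected cohort pending prompt DSMB review, and that review also considers whether the other cohort should pause.

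The 24-hour reporting these changes rely on already exists in 10.52. Sample size, the efficacy decision rules and patient treatment are unchanged. The price is an occasional pause in accrual and an unscheduled DSMB review, with a chance of at least one over 52 patients of about 41%, 65% or 93% at assumed related-death rates of 1%, 2% or 5%.
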